***Visit 3 & 4: Telephone support call (1 & 2 weeks - telephone)***

Phone based follow-up. Patients will converse with the study clinician (exercise physiologist/dietitian) to confirm compliance and identify any side effects or problems with the VLED.

***Visit 5: Clinic (1 month - face-to-face)***

A brief clinical appointment reassessing anthropometry, vitals and bio-impedance spectroscopy to confirm progress for patient feedback. Lifestyle consultation and session one of the program (Exercise, Planning, Doing, Tracking) will also be conducted.

***Visit 6: Clinic (2 months - face-to-face)***

A clinical appointment reassessing anthropometry and vitals to confirm progress for patient feedback. Lifestyle consultation to educate on transitioning from VLED to the weight maintenance diet (low GI, higher protein) and session one of the programme (Exercise, Planning, Doing, Tracking) will also be performed.

***Visit 7: Clinical assessment following VLED (3 months - face-to-face)***

The following examinations will be performed at this visit (not necessarily performed in this order):

- Insulin sensitivity (MINMOD) which incorporates an oral glucose tolerance test
- Total body fat & lean mass (DXA)
- Anthropometry & vitals
- Bio-impedance spectroscopy
- Blood markers
- 24 hr food recall
- Questionnaires
- Lifestyle consultation and confirm compliance with the weight maintenance diet
- 24 hour continuous blood glucose monitoring
- 24 hour central blood pressure monitoring
- Arrange referrals and/or follow up for handover to usual clinical care of weight maintenance and OSA.
- Sleep Study – performed one week after Visit 7. Participants assigned to CPAP will undergo a a one week CPAP washout prior to the sleep study

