### ***1.4 Background***

Obstructive Sleep Apnoea (OSA) affects over 3.5 million Australians with approximately 25% complaining of marked sleepiness and is one of the most common health complications of obesity and central adiposity.

OSA is a disorder which is characterised by repetitive episodes of partial (hypopnea) or complete (apnoea) upper airway obstruction occurring during sleep. These episodes often result in snoring and oxyhaemoglobin desaturations that are usually terminated by brief arousals from sleep. OSA is associated with hypertension, cardiovascular disease, depression, impaired quality of life, excessive daytime sleepiness (EDS) and

impaired neurobehavioral functioning. Continuous positive airway pressure (CPAP) is considered to be the ‘gold standard’ treatment for OSA. CPAP effectively alleviates obstructive episodes during sleep and has been found to improve parameters of sleepiness, cognitive performance and functional status in patients with severe OSA; however compliance with this treatment as well as other mechanical alternatives is problematic.

Numerous cross-sectional studies show insulin resistance in OSA as measured by Homeostasis Model Assessment (HOMA) or Oral Glucose Tolerance Test (OGTT). In addition, nocturnal glucose during sleep measured with continuous glucose monitoring (CGM) has been shown to be elevated in both non-diabetic and diabetic OSA.

Randomised Controlled Trials involving treatment of OSA with CPAP versus sham CPAP or conservative treatment have been equivocal with positive effects from CPAP being more evident with high compliance, in more severe OSA and in pre-diabetes. Apart from one small study no benefit has been shown in diabetes with respect to lowering of glycosylated haemoglobin (HbA1C).

One RCT explored the combined effect of weight loss and CPAP on cardio-metabolic parameters including insulin sensitivity and blood pressure and demonstrated greater improvements with combined treatments. No studies that have looked at CGM in weight loss and OSA treatment interventions.

The only major modifiable risk factor for sleep apnoea is obesity but the efficacy of weight loss in reducing OSA in individual patients is extremely variable. As gradual weight loss is the recommended treatment approach in OSA, many patients will not immediately show an improvement in the disturbing daytime sleepiness that is often the chief clinical complaint.

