***Visits 9 and 10– Lifestyle Support Call (7 and 9 months – phone call) - optional***

Phone based intervention lifestyle support call. Patients will converse with the study clinician and undertake a 24-hour food recall at visits 9 and 10 (7 months and 9 months and respectively). Visit 9 and 10 (phone calls) will cover the topic Maintaining the change while visit 10 will cover patient specific lifestyle re-assessment, goal setting and review.

Staff will schedule a date for Visit 11, approximately 3 months after visit 10.

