### ***24 hour Central Blood Pressure Monitoring***

Pulse wave analysis measures arterial stiffness by assessing peripheral and central blood pressure using a non-invasive device combined with an ambulatory 24 hour

brachial sphygmomanometer (Oscar 2™ system from SunTech Medical®). This is a portable automatic blood pressure machine, which takes measurements blood pressure, central pressure and arterial stiffness. Patients will be fitted with the machine by the study coordinator at baseline (Visit 2) and follow-up (Visit 8 and Visit 9). The patients will be asked to wear the device for 24 hours at each time point.

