#### ***Continuous Blood Glucose Monitoring***

A small sensor device (Medtronic Guardian) is worn by the participant for 24 hours. It is inserted comfortably under the skin, normally on the stomach, using a special insertion device secured with tape or a bandage, by a researcher, and the participant will be instructed on how to use it. The sensor measures glucose levels every few seconds and sends the information to a monitor that can be worn on a belt or in a pocket. Blood sugar levels will be checked to calibrate the device, using a regular glucometer and the widely used fingerprick technique, which only provides minimal discomfort. Potential side-effects include minor bruising, mild discomfort and a small risk of infection. The risk of any of these side effects is low.

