***Dissemination:***

Findngs will be disseminated via conferences, publications and media, as applicable. Patients will be informed of results of the study at the conclusion of the trial. Eligible authors will include investigators who are involved in the conception and design of the study, the conduct of the trial, the analysis of the results and authorship and

presentation of study findings. The full protocol will be added to the ANZCTR registry.

Appendix A: Time Frame for Study Visits	Visit number	2	3	4	5	6	7	8	9	10	11
	Month	0	1W	2W	1M	2M	3M	5M	7M	9M	1Y
Study Phase	Screen	Randomised Controlled					Follow up (optional consultations)				
Lifestyle Modification Phase		Very Low Energy Diet (VLED)				Trans- -ition	Low GI/High Protein Diet				
CPAP Phase		Randomised to CPAP or No CPAP					Usual Care for CPAP				
Eligibility & Informed Consent	X										
Randomisation to CPAP		X									
Reassessment of OSA and transfer into follow up phase with optional support							X				
Glucose Tolerance (OGTT, MINMOD)		X					X				X**
Total Body Fat & Lean Mass (DXA) & Bioimpedence		X					X				X
Anthropometry, Vitals		X			X	X	X				X
Blood Markers (Lipids,HbA1c,IGF1,IGFBP1)		X					X				X
24 Hour Testing (Continuous Central Blood Pressure & Continuous Glucose Monitoring)		X					X				X
4-day Food Diary		X						X			X
24-hr Food Recall					X	X	X		X	X	
Questionnaires		X					X				X
Sleep Study	X						X				X*
Lifestyle Consultation		X			X	X	X		X		X
Lifestyle Support Call			X	X				X		X	

\* PSG if clinically indicated by symptoms of obstructive sleep apnoea

\*\* If clinically indicated by elevated fasting blood glucose result

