3 month (Visit 7)	
 
• Full Assessment including dietary and exercise assessment and all other study procedures listed during a half day clinic visit
 
• Sleep study performed one week after Visit 7. Those using CPAP will have a one week washout prior to sleep study
 
• Measurement of glucose tolerance, insulin sensitivity, total body fat and lean mass
 
• Blood test, body measurements, bioelectrical impedance analysis, blood pressure, heart rate, wrist accelerometer and sensewear & diary and lifestyle consultation
 
• 24hr food recall
 
• 24 hour central blood pressure monitoring and 24 hour continuous blood glucose monitoring
 
•
 

5 month (Visit 8)	
 
• 2 hour clinic session OR Phone call/ Skype lasting 30- 60
 

– optional	
minutes
 
 
• Clinical assessment involving: anthropometry and vitals, bio-impedance spectroscopy, questionnaires and lifestyle consultation
 
• Session: Headspace and Food Choices
 
• 4 day food diary
 

7 month (Visit 9) – optional	
 
• Phone call or Skype lasting 30- 60 minutes
 
• 24 hour food recall
 
• Lifestyle consultation
 

9 month (Visit 10) – optional	
 
• Phone call or Skype lasting 15 - 30 minutes
 
• Session: Maintaining the Change
 

12 month (Visit 11) – optional	
 
• Full Assessment including dietary and exercise assessment and all other study procedures listed during a half day clinic visit
 
• Sleep study for those clinically indicated
 
• Measurement of fasting blood glucose (and glucose tolerance/ insulin sensitivity if clinically indicated), total body fat and lean mass
 
• Blood test, body measurements, bioelectrical impedance analysis, and lifestyle consultation.
 
• 24 hour central blood pressure monitoring and 24 hour continuous blood glucose monitoring
 
• 4 day food diary completed
 
• Study complete
 

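### The one-week CPAP washout starts at Visit 7, so 24-hour glucose and central BP recorders fitted then would capture the CPAP arm's first night off treatment; the BP procedure section names the wrong follow-up visits

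*Protocol*

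**What the plan says.** **Washout and sleep study.** Section 3.7, Visit 7, schedules the sleep study a week after the visit and states: "Participants assigned to CPAP will undergo a a one week CPAP washout prior to the sleep study". Appendix B repeats it at the 3-month visit: "Sleep study performed one week after Visit 7. Those using CPAP will have a one week washout prior to sleep study".

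**24-hour recordings at 3 months.** Both places also list 24-hour glucose and 24-hour central BP monitoring at Visit 7. Appendix A agrees: its row "24 Hour Testing (Continuous Central Blood Pressure & Continuous Glucose Monitoring") is marked at months 0, 3 and 12, which are Visits 2, 7 and 11. Appendix B describes Visit 7 as a full assessment with "all other study procedures listed during a half day clinic visit".

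**Wear time.** Section 3.8 says of the glucose sensor: "A small sensor device (Medtronic Guardian) is worn by the participant for 24 hours". The BP recorder is likewise worn for 24 hours after fitting.

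**Who fits the BP recorder, and when.** Section 3.8, 24 hour Central Blood Pressure Monitoring, says: "Patients will be fitted with the machine by the study coordinator at baseline (Visit 2) and follow-up (Visit 8 and Visit 9"). Visit 7 is not named there. In Section 3.7, Visit 8 is an optional contact at 5 months that may be by phone. Visit 9, at 7 months, is an optional "Phone based intervention lifestyle support call". Neither visit's own list includes 24-hour monitoring.

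**The concern.** Central blood pressure is the second hypothesis in Section 1.5, and 24-hour central BP and 24-hour glucose are named secondary outcomes. They are meant to show what CPAP adds to the diet at 3 months, so the CPAP arm needs to be on CPAP while they are recorded.

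The night is the part of the trace that matters most here. The only evidence on continuous glucose monitoring that Section 1.4 gives is about the night: "nocturnal glucose during sleep measured with continuous glucose monitoring (CGM) has been shown to be elevated in both non-diabetic and diabetic OSA". If treatment is withdrawn in one arm just before the single recorded night, the measurement no longer compares diet plus CPAP with diet alone. The expected direction of the error is towards no difference.

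The visit numbers in the BP procedure section raise a second problem. Followed literally, they would yield no 24-hour BP at 3 months. The model in Section 4 uses months 0 and 3, so no follow-up 24-hour BP value would enter it. By months 5 and 7, controls with persistent OSA may also have started CPAP, which Section 1.5 allows once the randomised phase ends.

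**Working it through.** The Protocol gives no calendar date for the start of the washout, so it has to be derived from the stated intervals.

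**Inputs**
- Sleep study: 7 days after Visit 7 (Section 3.7, Visit 7; Appendix B).
- Washout: 7 days, directly before the sleep study, CPAP arm only (same places).
- Recorder wear: 24 hours each (Section 3.8).
- Visit 7: half a day in clinic (Appendix B).
- Sample: 30 completers, 38 randomised, 1:1 (Sections 2.1 and 4).

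**Washout start.** Let day 0 be Visit 7.
- Sleep study = day 0 + 7 = day 7.
- Washout start = day 7 − 7 = day 0.
- Nights off CPAP before the sleep-study night: nights 0 to 6, which is seven nights.

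**Overlap with the recordings.** A 24-hour recording cannot finish within a half-day visit. A recorder fitted at Visit 7 runs from day 0 to day 1 and captures night 0, the first washout night.

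| Arrangement | Recording | Washout | Recorded nights in washout |
|---|---|---|---|
| Fitted at Visit 7, intervals as written | day 0 to 1 | day 0 to 7 | 1 of 1 |
| Fitted the day before Visit 7 | day −1 to 0 | day 0 to 7 | 0 of 1 |
| Washout counted from recorder removal, sleep study on day 8 | day 0 to 1 | day 1 to 8 | 0 of 1 |

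The overlap would also vanish if the sleep-study night itself counted as the seventh washout night (nights 1 to 7). The Protocol specifies none of these alternatives.

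**Participants exposed.** CPAP arm = 30 / 2 = 15 completers, or 38 / 2 = 19 randomised. The control arm's recorded night is unchanged.

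**BP fitting visits, side by side**

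| Source | Follow-up 24-hour BP |
|---|---|
| Section 3.8, BP monitoring | Visits 8 and 9 = months 5 and 7 |
| Section 3.7, Visit 7 | month 3 |
| Appendix A | months 3 and 12 (Visits 7 and 11) |
| Appendix B | months 3 and 12 (Visits 7 and 11) |

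Measured from the 3-month endpoint, Visit 8 is 5 − 3 = 2 months late and Visit 9 is 7 − 3 = 4 months late. The conflict concerns BP only, because the glucose-monitoring section names no visits.

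**Primary outcome.** The OGTT is done during Visit 7, before any night off CPAP.

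**The case against.** The strongest reply is that the overlap turns on one day and on loose wording. If the 24-hour recordings count as part of Visit 7, the week and the washout could be read as starting once they are finished, and the overlap is then zero. Only the sleep study is put back by a week, which suggests that the other 3-month measures were meant to be taken on treatment. The half-day description is also a weak basis for exact timing, since it covers 24-hour monitoring that cannot fit into half a day.

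That reading is possible, and it may be what was intended. But no sentence says it, and nothing tells the CPAP arm to continue until the recorders come off. Staff who apply the stated intervals would stop CPAP at Visit 7.

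The BP visit numbers are probably a clerical slip: three other places have month 3, and a recorder cannot be fitted by phone. It is therefore unlikely that month 3 would be missed altogether. The contradiction is still in the current text.

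The impact is unquantified. Section 1.4 does not say how fast glucose or central BP changes after CPAP is stopped, and one night may not remove the effect. That stands and limits the seriousness of the point, as does the fact that only two secondary outcomes of a pilot are involved.

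Finally, moving the BP fittings to Visits 7 and 11 leaves one loose end: the Visit 11 list in Section 3.7 omits both 24-hour recordings, although Appendices A and B include them. That inconsistency already exists and does not undermine the correction.

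**Conclusion.** The point holds on both counts and should be fixed. As scheduled, the washout begins at Visit 7, and recorders put on at that visit would capture one night out of one off CPAP, in the CPAP arm only (up to 15 completers or 19 randomised). This rests on two assumptions: that one week means seven days, and that the recorders are fitted at Visit 7. The Protocol's timings imply the overlap but do not state it. The bias would tend towards no difference in 24-hour glucose and 24-hour central BP, and its size cannot be derived from the document.

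The contradiction over the BP fitting visits needs no inference: Section 3.8 gives months 5 and 7, against month 3 in Section 3.7 and both appendices. The primary outcome is not affected by either problem.

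**What to change.** 1. In Section 3.7 (Visit 7) and Appendix B, state that CPAP continues until both 24-hour recorders have been removed. Count the one-week washout from removal and hold the sleep study on day 8. The alternative is to fit the recorders the day before Visit 7 and leave the sleep study on day 7.
2. In Section 3.8, 24 hour Central Blood Pressure Monitoring, change the follow-up fitting visits from 8 and 9 to 7 and 11.
3. While editing, bring the Visit 11 list in Section 3.7 into line with Appendices A and B on the 12-month recordings.
4. As a lesser clarification, say at Visit 2 that the baseline recordings finish before the diet and CPAP start, since no day is fixed there.

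For items 1 and 2 the cost is a one-day shift of the sleep study, or one short extra attendance for fitting if the alternative is chosen, plus corrected visit numbers. No new test is needed. A 3-month recording taken off CPAP cannot be recovered afterwards, so the change has to come before participants reach Visit 7.

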***Visit 8 – Clinical Monitoring (5 months – phone call or face to face) – optional***

The following examinations will be performed at this visit (may not necessarily be performed in this order). At 5 months, (visit 8) the 4-day food diary will be collected to ensure compliance with the dietary prescription following completion of the VLED.

- Anthropometry & Vitals
- 4-day food diary
- Questionnaires
- Lifestyle consultation and session two of the program (Food Thoughts and Lapses)

Staff will schedule a date for Visit 9 and 10.

***Visits 9 and 10– Lifestyle Support Call (7 and 9 months – phone call) - optional***

Phone based intervention lifestyle support call. Patients will converse with the study clinician and undertake a 24-hour food recall at visits 9 and 10 (7 months and 9 months and respectively). Visit 9 and 10 (phone calls) will cover the topic Maintaining the change while visit 10 will cover patient specific lifestyle re-assessment, goal setting and review.

Staff will schedule a date for Visit 11, approximately 3 months after visit 10.

***Visit 11 – Outcomes collection (12 months - face-to-face) - optional***

The following examinations will be performed at this visit (may not necessarily be performed in this order).

- Fasting blood glucose test, if results indicate patient remains in a pre-diabetic state (5.5-7 mmol/L) an oral glucose tolerance test is clinically indicated and will be requested by study staff.
- Total Body Fat & Lean Mass (DXA)
- Anthropometry & Vitals
- Bio-impedance spectroscopy
- Blood markers
- 4-day food diary
- Questionnaires
- Lifestyle consultation
- Sleep Study: for symptomatic untreated individuals
- Patients who have continued using CPAP since the 3 month timepoint will be requested to bring their device memory card for download and confirm compliance.

***Booster Sessions***

Patients presenting with low adherence to the weight loss program (<75% adherence as determined by food diary or 24 hour food recall) or demonstrating a need for additional support via more frequent anthropometry may be offered to participate in face-to-face sessions instead of skype/phonecall sessions. This will be at the

discretion of the study physicians and study coordinator where a consensus must be met based on weight loss and patient compliance monitoring.

## **3.8 Study Procedures and Assessments**

### ***Personnel training***

*Relevant study personnel will be trained by investigators on outcome collection.*

### ***Informed consent***

Each potentially eligible participant will be informed of the study's objectives and overall requirements using the Patient Information Sheet and Informed Consent Form. A copy of the form will be provided for the participant. If the volunteer is willing to participate in the study, they will be requested to provide written and witnessed informed consent prior to participation in the trial.

### ***Anthropometry***

Anthropometric measurements will be taken at every meeting. These will include:

- Height (at screening only)
- Weight
- BMI
- Neck circumference (triplicate)Waist circumference (triplicate)

### ***Office Blood Pressure***

- Blood pressure (BP), and heart rate (HR) will be recorded at each contact visit including the termination visit should it occur, following European Society of Hypertension guidelines.
- Throughout the study, BP will be measured using the same type of device and a standard sized BP cuff will be used, except a larger and smaller cuff will be used for large arms (>32cm) and small arms, respectively.
- BP will be measured on both arms at baseline to detect possible differences. In this instance, the arm with the higher value will be taken as the reference.
- At least 2 BP measurements will be taken, in the sitting position, spaced 1-2 minutes apart, and additional measurements if the first two are quite different.

### ***24 hour Central Blood Pressure Monitoring***

Pulse wave analysis measures arterial stiffness by assessing peripheral and central blood pressure using a non-invasive device combined with an ambulatory 24 hour

brachial sphygmomanometer (Oscar 2™ system from SunTech Medical®). This is a portable automatic blood pressure machine, which takes measurements blood pressure, central pressure and arterial stiffness. Patients will be fitted with the machine by the study coordinator at baseline (Visit 2) and follow-up (Visit 8 and Visit 9). The patients will be asked to wear the device for 24 hours at each time point.

### ***Wrist accelerometer***

Sleep and wake periods and activity will be gauged using a commercially available device (Respironics Actiwatch2). We will also be using this device's raw activity counts as an objective measure of physical activity levels.

### ***Glucose control***

#### ***Oral Glucose Tolerance Test***

Glucose tolerance will be assessed by 2 hour blood glucose level following a 75g oral glucose load. A total of 10ml of blood will be collected at each time point (baseline, 3 months and 12 months).

#### ***Insulin Sensitivity***

Insulin sensitivity will be assessed by modified minimal model (MINMOD) analysis of multiple measurements of insulin, glucose and c-peptide (at 0, 10, 20, 30, 60, 90, 120, 150 and 180 mins) after a 75g oral glucose load, using a previously published method (Dalla-Man et al, Diabetes 2005; 54:3265-3273). A total of approximately 100ml of blood will be collected at each time point (baseline, 3 months and 12 months). This measurement will incorporate measurement of glucose tolerance.

#### ***Continuous Blood Glucose Monitoring***

A small sensor device (Medtronic Guardian) is worn by the participant for 24 hours. It is inserted comfortably under the skin, normally on the stomach, using a special insertion device secured with tape or a bandage, by a researcher, and the participant will be instructed on how to use it. The sensor measures glucose levels every few seconds and sends the information to a monitor that can be worn on a belt or in a pocket. Blood sugar levels will be checked to calibrate the device, using a regular glucometer and the widely used fingerprick technique, which only provides minimal discomfort. Potential side-effects include minor bruising, mild discomfort and a small risk of infection. The risk of any of these side effects is low.

